#### 9.2.5.1. Adverse events

There will be no attempt to impute the following

- Missing AE start dates
- AE start dates missing the year
- Partial/missing AE end dates

Table 1 explains the abbreviations used.

	Day	Month	Year
Partial Adverse Event Start Date	<not used=""></not>	AEM	AEY
Treatment Start Date (TRTSTD)	<not used=""></not>	TRTM	TRTY

Table 2 describes the possible combinations and their associated imputations. The upper text indicates the imputation (NC, A, B, C etc) and the lower text the relationship of the AE start date to the treatment start date (TRTSTD).

	AEM MISSING	AEM < TRTM	AEM = TRTM	AEM > TRTM
AEY MISSING	NC	NC	NC	NC
	Uncertain	Uncertain	Uncertain	Uncertain
AEY < TRTY	(D)	(C)	(C)	(C)
	Before TRTSTD	Before TRTSTD	Before TRTSTD	Before TRTSTD
AEY = TRTY	(B)	(C)	(B)	(A)
	Uncertain	Before TRTSTD	Uncertain	After TRTSTD
AEY > TRTY	(E)	(A)	(A)	( A )
	After TRTSTD	After TRTSTD	After TRTSTD	After TRTSTD

#### Table 2Imputation algorithm

The legend to the above table is shown in Table 3.

#### Table 3Imputation algorithm legends

Relationship	
Before TRTSTD	Indicates AE start date prior to Treatment Start Date
After TRTSTD	Indicates AE start date after Treatment Start Date
Uncertain	Insufficient to determine the relationship of AE start date to Treatment Start Date
Imputation calculation	
NC / Blank	No convention/imputation
(A)	01MONYYYY
(B)	TRTSTD+1
( C )	15MONYYYY
(D)	01JULYYYY
(E)	01JANYYYY

Few examples are shown in Table 4.

Table 3	Example scena	nrios		
Partial AE start date	Treatment start date	Relationship with TRTSTD	Imputation Calculation	Imputed Date
12mmyyyy	20OCT2001	Uncertain	NC	<blank></blank>
ddmmm2000	20OCT2001	Before	(D)	01JUL2000
ddmmm2002	20OCT2001	After	(E)	01JAN2002
ddmmm2001	20OCT2001	Uncertain	(B)	21OCT2001
ddSEP2001	20OCT2001	Before	(C)	15SEP2001
ddOCT2001	20OCT2001	Uncertain	(B)	21OCT2001
ddNOV2001	20OCT2001	After	(A)	01NOV2001

If imputed start date is greater than the end date of the adverse event, when end date is available, the imputed start date will be set equal to the end date

#### 9.2.5.2. Concomitant medication date imputation

The imputation of the start date of concomitant medication will follow the same conventions as for AE date. Partial/missing concomitant medication end dates will not be imputed.

#### 9.2.5.3. Diagnosis and extent of cancer

The following variables require imputation when incomplete:

- a. Date of initial diagnosis of primary site of cancer
- b. Date of first recurrence/relapse
- c. Date of most recent recurrence/relapse

Missing day is defaulted to 15 and missing month and day is defaulted to January 01, unless any of the following applies:

#### First recurrence/progression date:

• If day is missing AND occurred in the same month of the most recent relapse/progression, then day of first recurrence/progression will be imputed as the minimum between 15 and day of the most recent relapse/progression.

#### Most recent relapse/progression date:

- If day is missing AND occurred in the same month of the first recurrence/progression, then day of most recent relapse/progression will be imputed as the maximum between 15 and day of first recurrence/progression.
- If month and day are missing AND occurred in the same year of the first recurrence/progression, then month and day of most recent relapse/progression will be imputed as the maximum between January 01 and month and day of first recurrence/progression

#### 9.2.5.4. Anti-cancer therapy

#### Prior therapies

- Start date: The same rule which is applied to the imputation of AE/concomitant medication start date will be used with the exception that: for scenario (B) will be replaced to be treatment start date -1.
- End date:
  - $\circ$  Imputed date = min (reference end date, DEC 31), if month and day are missing.
  - Imputed date = min (reference end date, last day of the Month), if day is missing.
  - Reference end date will be treatment start date.
- If the end date is not missing and the imputed start date is after the end date, use the end date as the imputed start date.
- If both the start date and the end date are imputed and if the imputed start date is after the imputed end date, use the imputed end date as the imputation for the start date

#### Post therapies

#### • Start date:

- If Day is missing, then impute to the max (reference start date, first day of the month).
- Day and month are missing then impute to the max(reference start date, Jan 1)
- $\circ$  Reference start date will be last date of study treatment administration + 1.
- End date: No imputation

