#### 9.2.5. Imputation of Partial Dates

Only the year of birth is being collected within the EDC system, subject birth date and month will be defaulted to '30/JUN'. For example, if birth year is 1989 then birthdate will be 30/Jun/1989.

With the exception of new anti-cancer start date on the time to event (PFS, TTP, OS) analysis dataset and exposure end date on the Exposure analysis dataset, imputed dates will not be stored on datasets.

Imputed dates will not be displayed in listings. However, where necessary, display macros may impute dates as temporary variables for the purpose of sorting data in listings only. In

addition partial dates may be imputed for 'slotting' data to study time periods (see Section 9.3) or for specific analysis purposes as outlined below.

The partial date imputation will follow ADaM conventions. The ADaM approach is to populate the numeric date variables with the imputed date and add a flag variable to the dataset that indicates the level of imputation.

The flag variable can contain the values: blank, 'D', 'M', 'Y'.

blank: indicates that no imputation was done

D='Day': indicates that the day portion of the date is imputed

M='Month': indicates that the month and day portions of the date are imputed

Y='Year': indicates that the entire date (year, month, and day) is imputed

Example of Date Variables:

XYZD\_ - character date variable

XYZDT - numeric date variable

XYZDTFL - flag variable

Details on imputing partial dates for specific datasets are outlined below.

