#### 9.2.5.7. Assessment date of tumor assessments

All investigation dates (e.g. X-ray, CT scan) must be completed with day, month and year.

If one or more investigation dates are incomplete but other investigation dates are available, this/these incomplete date(s) are not considered for calculation of the assessment date and assessment date is calculated as the latest of all investigation dates (e.g. X-ray, CT-scan) if the overall lesion response at that assessment is CR/PR/SD/UNK. Otherwise – if overall lesion response is progression – the assessment date is calculated as the earliest date of all investigation dates at that evaluation number. If all measurement dates have no day recorded, the 1st of the month is used.

If the month is not completed, for any of the investigations, the respective assessment will be considered to be at the date which is exactly between previous and following assessment. If a previous and following assessment is not available, this assessment will not be used for any calculation.

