#### **Progression-Free Survival (PFS)**

Progression-Free survival (PFS) is defined as the interval between the date of first dose of protocol therapy and the earliest date of disease progression or death due to any cause.

Progression will be based on the investigator assessment. Subjects are considered to have progressive disease if they have documented progression based on radiologic assessment as determined by investigator review (defined in protocol section 10). The date of death should be taken from the Death page in eCRF. Death on study due to any cause will be included. For subjects who do not progress or die, progression-free survival will be censored at the date of last adequate assessment prior to starting new anti-cancer therapy.

If there is no adequate baseline assessment, the subjects will be censored at their treatment start date. Subjects without any adequate post-baseline tumor assessments will also be censored at their treatment start date.

For subjects who receive subsequent anti-cancer therapy the following rules will apply:

- If the start date of the anti-cancer therapy is partial (i.e. either missing the day but has the month and year available or missing both day and month), the imputation rules described in Section 9.2.5.4 will be applied. No imputation will be made for completely missing dates.
- If anti-cancer therapy is started without documented disease progression or is started prior to documented disease progression, then PFS will be censored at the date of the last adequate assessment that is no later than the date of initiation of anti-cancer therapy (i.e. if an assessment occurs on the same day as the start of new anti-cancer therapy the assessment will be used as it will be assumed the assessment occurred prior to the administration of new anti-cancer therapy).
- If a subject has only a baseline visit or does not have an adequate assessment that is no later than the date of initiation of anti-cancer therapy, PFS will be censored at the treatment start date.

If a subject has neither progressed nor died nor started new anti-cancer therapy, then PFS will be censored at the date of the last adequate assessment defined as an assessment where the Investigator determined is CR, or PR, or SD. The date of assessment will be used as the censoring date.

A summary of the assignments for progression and censoring dates for PFS are specified in the following table.

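### In a limited set of patients, the SAP's rules for a partly dated new therapy and for a scan with no month can turn a documented progression into a censored PFS or TTP time

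*SAP*

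**What the plan says.** **New therapy.** SAP 9.2.5.4 (Post therapies) gives two rules. With the day missing: "If Day is missing, then impute to the max (reference start date, first day of the month". With day and month missing: "Day and month are missing then impute to the max(reference start date, Jan 1". It adds: "Reference start date will be last date of study treatment administration + 1".

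The imputed date is not only for listings. SAP 9.2.5 keeps imputed dates off the datasets, but this date is one of its exceptions: "With the exception of new anti-cancer start date on the time to event (PFS, TTP, OS) analysis dataset". SAP 10.2 (PFS) then calls on the imputation: "If the start date of the anti-cancer therapy is partial (i.e. either missing the day but has the month and year available", or the month as well, 9.2.5.4 applies. It continues: "If anti-cancer therapy is started without documented disease progression or is started prior to documented disease progression, then PFS will be censored", at the last adequate assessment no later than the therapy start, or at treatment start if there is none. Table 5 repeats this, and its footnote 3 counts a same-day progression and new therapy as a progression. TTP takes its event and censoring assignments from Table 5. Protocol 9.8.2.3 describes PFS censoring only for patients who neither progress nor die.

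**Scan dates.** SAP 9.2.5.7 requires complete dates for all investigations. It ignores an incomplete date when other investigations at that assessment are dated. An assessment with no month is placed midway between its neighbours, and: "If a previous and following assessment is not available, this assessment will not be used for any calculation". Progression is not exempted.

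Neither document plans a sensitivity analysis for either rule.

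**The concern.** The new-therapy rule picks the earliest admissible day, and the order of that day against the progression scan decides whether the patient counts as an event. A progression seen on a dated scan can therefore be overridden by an assumed therapy date. If new therapy starts after the last dose, the imputed day is never later than the true one. The rule can then turn a true event into a censoring but not a true censoring into an event. The censoring would also be informative, because the patients censored are those who have just progressed.

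The scan rule has a related weakness. Progression ends protocol therapy (Protocol 8.1), so the progression scan is normally the last one. It is thus the scan least likely to have the following assessment that the rule demands.

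What is at stake is the PFS and TTP curves, and DoR for the discarded scan, in cohorts of 10 to 20 patients where one reclassified patient can move a median.

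**Working it through.** The plan states no figure that depends on these rules, so there is none to reproduce. I applied the rules directly.

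**1. Formula.** Let L be last dose, P the progression scan, T the true start of new therapy and A the imputed start.

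- Day missing: A = max(L + 1, first of T's month).
- Day and month missing: A = max(L + 1, 1 January of T's year).
- Event at P if P ≤ A (footnote 3 covers the tie). Otherwise censored at the last CR, PR or SD on or before A, or at treatment start.

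**2. Who is exposed.** If L = P or L = P − 1, then A ≥ L + 1 ≥ P and the event stands. Exposure needs L ≤ P − 2 and the first day of the recorded month or year before P. The protocol allows such gaps. Section 7.1 asks for a disease evaluation when therapy ends for any reason, and still wants one after removal for clinical or laboratory progression. Section 4.1.3 requires permanent discontinuation only after more than 28 days' interruption.

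**3. Worked patient (assumed dates).** First dose 1 Jan 2018, SD 26 Feb (31 + 26 = day 57), PD scan 20 Apr (31 + 28 + 31 + 20 = day 110).

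| Last dose | True new therapy | Recorded as | Imputed | PFS result |
|---|---|---|---|---|
| 8 Apr | 27 Apr | full date | none | event, day 110 |
| 8 Apr | 27 Apr | April | 9 Apr | censored, day 57 |
| 19 Apr | 27 Apr | April | 20 Apr | event, day 110 |
| 10 Mar | 3 May | May | 1 May | event, day 110 |
| 10 Mar | 15 Sep | year only | 11 Mar | censored, day 57 |

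**4. Share of exposed events recoded.** Assume L ≤ P − 2, P uniform over a 365-day year, and T = P + k days.

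Day missing: in a month of n days, the n − k − 1 scan dates from the 2nd to day n − k are recoded (none if that is negative).

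- k = 1: (365 − 12×2)/365 = 341/365 = 93%
- k = 7: (365 − 12×8)/365 = 269/365 = 74%
- k = 14: (365 − 12×15)/365 = 185/365 = 51%
- k = 21: (365 − 12×22)/365 = 101/365 = 28%
- k = 28: (7×2 + 4×1)/365 = 18/365 = 5%

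Day and month missing: (365 − k − 1)/365, which is 363/365 = 99% at k = 1 and 274/365 = 75% at k = 90.

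Enumerating every date for gaps of 2, 7, 14 and 28 days gave the same shares. For gaps of 0 and 1 day the share was 0%.

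**5. Scan with no month.** Take the same patient, with no month on the progression scan, no other dated investigation at that assessment and no later scan. The assessment is not used. If the patient is alive, or started new therapy first, PFS is censored at day 57. If the patient dies with no earlier new therapy, Table 5 gives an event at the death date, later than day 110.

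**6. Effect on a median (illustration only).** Assume 10 patients with PD at week 8 (5), week 16 (3) and week 28 (2). S(8) = 5/10, so the median is 8 weeks at the first time S reaches 0.50, or (8 + 16)/2 = 12 by the midpoint convention. Recode two week-8 patients as censored at Day 1: S(8) = 5/8 = 0.625, S(16) = 2/8 = 0.25, median 16. Recode one: S(8) = 5/9 = 0.56, S(16) = 2/9 = 0.22, median again 16.

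**The case against.** The strongest reply is that the ordinary progressor is already protected. Dosing is continuous, scheduled scans fall in the last days of a cycle, and a patient dosed to the scan is covered by the last-dose-plus-one floor and the tie rule. That stands, and it confines the first problem to patients who were off drug before the scan.

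Several stronger readings are tempting, and the documents do not support them.

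- **That progressions are lost on a wide scale.** Three-monthly follow-up makes partial therapy dates conceivable, but neither document says how complete those dates are. The shares in step 4 are conditional on exposure and do not estimate bias in this trial.
- **That the median PFS would double.** The example sits on the S = 0.50 boundary, and its one or two recoded patients in ten have no source. Under the midpoint convention the move is 12 to 16 weeks. Week 8 is also a scheduled scan normally taken on drug, so the recoded patients would have to have stopped early.
- **That 9.2.5.7 contradicts itself.** Its month-missing condition can be read as any one investigation lacking a month, which would clash with the paragraph before it. It can equally be read as no investigation having one, a natural fallback. This is an ambiguity, and two programmers could resolve it differently.
- **That a discarded progression always ends as a censoring.** Death without earlier new therapy makes it a late event.

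The reply also notes that these endpoints are descriptive, that no formal hypothesis is tested (SAP 8.4), and that the study was already declared futile (SAP 4.3). This lowers the stakes but does not make the rules right.

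**Conclusion.** The point holds in this limited form. As written, the SAP can recode a documented progression as censored when dosing stopped at least two days before the scan and the earliest date fitting a partial therapy record falls before it. It can also discard a progression scan that has no month and no later assessment.

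The per-patient effect can be large (event at day 110 against censoring at day 57). The effect on the trial cannot be sized, because the number of partial dates is unknown. PFS and TTP are affected, and DoR through the discarded scan only. ORR and the two-stage rule do not depend on these dates. The change is worth making because it is cheap and the rules are explicit, but no primary conclusion rests on it. The assumptions are that new therapy starts after the last dose and, for the shares, that scan dates are spread evenly over the year.

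**What to change.** Amend two places before the final database lock.

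(a) **SAP 9.2.5.4 and 10.2, for PFS and TTP.** When a documented progression falls within the recorded partial period of the new therapy (the month, or the year if only that is known), do not let the imputed date override it. Count the progression as an event at its scan date. Report the current earliest-date rule as a sensitivity analysis, because the changed rule could count a progression that truly followed new therapy.

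(b) **SAP 9.2.5.7.** State that the month-missing rule applies only when no investigation at that assessment has a usable date. Keep a progression with no following assessment as an event. Date it between the previous assessment and the treatment discontinuation date or, if discontinuation came before the scan, the earliest later dated record such as new therapy or death. Flag the date as imputed. Avoid using a last-contact date, which may be months later.

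The cost is two SAP passages, a small programming change, one extra sensitivity run and possibly a slight overcount of events.

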#### 9.2.5.5. Last contact or death date(s)

All dates must be completed with day, month and year. If the day is missing, the 1st of the month will be used for incomplete death dates or dates of last contact.

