10.8 Survival Follow-Up

Patients who have discontinued protocol therapy will be followed for Survival status. The investigator site will collect and report Survival follow-up in the eCRF every 3 months, which would include the patient's survival status and any antineoplastic therapies taken since discontinuation of protocol therapy, until death, lost to follow-up, or withdrawal of consent from survival follow-up occurs or final cut-off for survival analysis.

The date and cause of death should be recorded in the eCRF.

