#### Table 5: Assignments for Progression and Censoring Dates for PFS Analysis

Situation	Date of Event (Progression/Death) or Censoring	Outcome Event (Progression/Death) Or Censored
Progression documented between scheduled visits	Date of assessment of progression 	Event
No progression (or death)	Date of last 'adequate' assessment of response 	Censored
New anticancer treatment started (prior to documented disease progression). 	Date of last 'adequate' assessment of response  (on or prior to starting anti-cancer therapy)	Censored
Death without PD	Date of death	Event

 The earliest of (i) Date of radiological assessment showing new lesion (if progression is based on new lesion); or (ii) Date of radiological assessment showing unequivocal progression in non-target lesions, or (iii) Date of last radiological assessment of target lesions (if progression is based on increase in sum of target lesions)

- 2. An adequate assessment is defined as an assessment where the Investigator] determined response is CR, PR, or SD.
- 3. If PD and New anti-cancer therapy occur on the same day assume the progression was documented first e.g., outcome is progression and the date is the date of the assessment of progression). If anti-cancer therapy is started prior to any post-baseline adequate assessments, censoring date should be the treatment start date.

PFS will be summarized using a Kaplan-Meier survival curve. The Kaplan-Meier estimate for the median progression-free survival time and the first and third quartiles will be presented, along with a naive approximate 90% confidence interval if there are a sufficient number of progressions or deaths. This analysis will be repeated on the mITT population as a supportive analysis of PFS.

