#### **Overall Survival (OS)**

Overall Survival (OS) is defined as the time from the first dose of the study medication until death due to any cause. The length of this interval is calculated as the date of death minus the date of treatment start plus one. Subjects who have not died at the time of the analyses will be censored at the date of last contact (as recorded in the eCRF). Last date of contact will be defined as the maximum date of any visit date or the survival follow-up date. Only subject contacts recorded in the eCRF can be used for the calculation of last date of contact.

OS will be summarized using Kaplan-Meier survival curves. The Kaplan-Meier estimate for the median OS time and the first and third quartiles will be presented, along with a naïve approximate 90% confidence interval if there are a sufficient number of deaths.

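### The SAP dates a death with a missing day at the 1st of the month, with no floor at the last date known alive, so impossible date sequences can arise

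*SAP*

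**What the plan says.** SAP 9.2.5.5 opens with a collection requirement, "All dates must be completed with day, month and year", and then gives the fallback: if the day is missing, the 1st "of the month will be used for incomplete death dates or dates of last contact". The section contains no other rule. Protocol 10.8 asks sites for the date itself: "The date and cause of death should be recorded in the eCRF".

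SAP 10.2 (OS) uses the death date directly: "The length of this interval is calculated as the date of death minus the date of treatment start plus one". For patients still alive the censoring date has a safeguard: "Last date of contact will be defined as the maximum date of any visit date or the survival follow-up date".

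For PFS, the prose in SAP 10.2 takes "the interval between the date of first dose of protocol therapy and the earliest date of disease progression or death due to any cause". Table 5 assigns dates row by row. The row "Progression documented between scheduled visits" takes the date of the progression assessment. The date of death is used only in the row for death without progression.

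Other imputed dates in the SAP are bounded. For post-treatment anti-cancer therapy, SAP 9.2.5.4 has "If Day is missing, then impute to the max (reference start date, first day of the month"), where the reference is the day after last dose. An imputed last dose cannot precede treatment start (9.2.5.6). An imputed most recent relapse is held at or after the first recurrence when both fall in the same month or year (9.2.5.3). An imputed AE start is capped at the AE end date (9.2.5.1).

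**The concern.** The 1st is the earliest day in any month, so the imputed death is never later than the true one and is usually earlier. With no floor, nothing stops it from preceding a day on which the same patient attended a visit, had a scan or took a dose. Three kinds of impossible result follow: death before a documented alive date, OS shorter than PFS, and survival of zero or negative length.

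The cohorts hold 10 to 20 patients, so a single such record would be conspicuous and awkward to defend. SAP 9.2.5 says that imputed dates are not shown in listings, so a reader checking the listings would not see the cause. The same death date also feeds the split of deaths at 28 days after last dose (SAP 11.4). Because neighbouring dates carry bounds, the gap for death looks like an omission rather than a choice.

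**Working it through.** The plan gives no figure for this rule, so there is none to reproduce. The check applies the SAP rule and the OS formula to dates.

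**Inputs from the documents.** Missing day is set to the 1st (SAP 9.2.5.5). OS = death − start + 1 (SAP 10.2). With documented progression, PFS runs to the progression assessment (SAP Table 5). Survival follow-up is every 3 months (Protocol 10.8).

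**Assumed inputs.** Day of death uniform over the calendar; the gap from last alive contact to death; the time from progression to death; the share of deaths with the day missing. None of these is given in the documents, so ranges are shown.

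**1. Worked case A.** Start 8 Jan 2018, progression 5 Mar, seen alive 20 Mar, died 27 Mar, day missing. Imputed death is 1 Mar.
- Imputed OS = 52 + 1 = 53 days; true OS = 78 + 1 = 79 days.
- Last day seen alive = 71 + 1 = day 72, which is 19 days after the imputed death.
- PFS by Table 5 = 56 + 1 = 57 days, so OS is 4 days shorter than PFS.
- If the prose definition (earliest of progression or death) is programmed literally, PFS also becomes 53 days and the error moves into PFS.

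**2. Worked case B.** Start 12 Mar 2018, seen alive 20 Mar, died 27 Mar, day missing. Imputed OS = −11 + 1 = −10 days; true OS = 15 + 1 = 16 days. A start on the 2nd of the month of death gives exactly 0.

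**3. Size per affected death.** The shift is day of month − 1, averaging (m − 1)/2 in a month of m days. Over a four-year calendar of 1,461 days: (868 × 15 + 480 × 14.5 + 84 × 13.5 + 29 × 14) / 1,461 = 21,520 / 1,461 = 14.7 days, or 14.7 / 30.4375 = 0.48 month. The maximum is 30 days, and the shift is never upward.

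**4. How often an affected death gives an impossible sequence (simulated).**
- Imputed death before the last alive contact: about 49% if that contact was 1–28 days before death, and about 15% if 1–91 days before (gaps uniform).
- OS shorter than PFS, among affected deaths with documented progression: about 36%, 14% and 8% for a mean progression-to-death time of 30, 91 and 183 days (exponential).

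**5. Effect on median OS.** Simulated with n = 10 or 20, exponential OS with median 4 to 12 months, and no censoring.

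| Assumed share of deaths with day missing | Shift in median OS |
|---|---|
| 5% | about −0.7 day |
| 10% | about −1.4 days |
| 25% | about −3.6 days |
| 100% | about −14.6 days |

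**6. With a floor at the last date known alive.** Case A: OS = 72 days, no longer below PFS (57). Case B: OS = 8 + 1 = 9 days. The mean downward shift per affected death falls from 14.7 to about 9.7 days (contact 1–28 days before death) or 13.2 days (1–91 days).

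**The case against.** The rule is a last resort. Complete dates are required, the eCRF asks for the date of death, and data cleaning under Protocol 12 aims to resolve inconsistencies that would affect the analysis; a death dated before a later scan is one. The separate dataset specifications mentioned in SAP 9.2 may contain a floor. OS is secondary and descriptive, SAP 8.4 says that no hypothesis is tested, no cohort decision uses OS, and the study had already been declared futile after stage 1 (SAP 4.3). The 1st of the month also shortens survival, so it cannot flatter the drug.

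Most of this stands, and it limits the size of the problem. It does not supply a bound. The SAP is where Protocol 9.8.2.3 sends the reader for event dates, and it states none. The specifications are not available here, so it cannot be said that the programming lacks a floor.

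Two wider readings should be resisted. A reader might infer that OS is generally shorter than PFS under this rule. That needs progression, or a PFS-censoring assessment, dated after the 1st of the month of death; for a death without progression that counts as the PFS event, both endpoints use the same imputed date. A reader might also infer that censoring times of living patients suffer equally. They do not: the maximum in SAP 10.2 lets any later visit date override a follow-up date set to the 1st.

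**Conclusion.** The point holds as a missing floor that permits impossible dates. Death before a documented alive date, OS shorter than PFS, and zero or negative OS all follow from the SAP text by arithmetic and need no assumption beyond a missing day and the right calendar position.

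The size is modest. Each affected death is about 15 days early on average and at most 30, taking the day of death as uniform. A reader might infer a material downward bias in OS. The documents do not support that: they do not say how many death dates are partial, complete dates are required, and at an assumed share of 10% or less the median moves by under 2 days. No primary result or decision rule is touched. This is a small correction worth making because it is cheap and prevents indefensible records.

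**What to change.** Add one sentence to SAP 9.2.5.5: when only the day of death is missing, impute the later of the 1st of the recorded month and the last date on which the patient was documented alive, kept within the recorded month. Dates documented alive are visits, tumour assessments, doses, and follow-up contacts at which status was recorded as alive.

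Two details of wording matter:
- Exclude the contact that reported the death. With follow-up every 3 months it can come well after the death, and using it as a floor would date the death too late.
- Use the last alive date itself, not the day after. A patient can die on the day of a visit or dose, and a next-day rule could push the death into the following month. If an alive date falls after the recorded month of death, the records conflict and should be queried.

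Because the first dose is itself a date documented alive, OS is then at least 1 day. The floor removes the impossible sequences but only part of the downward shift. Incomplete last-contact dates need no change beyond the maximum already defined in SAP 10.2 (OS). The cost is one line of text and one line of derivation code.
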